7.2 Lifestyle Restrictions

7.2.1 Reproductive Restrictions

All WOCBP must have a negative urine pregnancy test at the Screening Visit and the Baseline Visit prior to randomization in the study and must not intend to become pregnant during the study.

Women of childbearing potential must use an effective method of birth control during study participation. Acceptable methods include the use of at least one of the following: intrauterine device, hormonal (oral, injection, patch, implant, ring) contraception, barrier with spermicide (condom, diaphragm), a vasectomized partner, or abstinence.

Refer to [Section 8.8](#) for more information on management of subjects who become pregnant during the study or up until 30 days after the last dose of the IP.

7.3 Informed Consent

The study will be introduced to potentially eligible treatment-experienced patients with DED by a care provider known to the patient. Prior to conducting any screening activities, a complete discussion of the purpose of the study, IPs to be tested, and study activities and assessments will be explained and reviewed with the patient. The patient will be given ample time to ask any questions and will undergo a formal informed consent process, to discuss potential benefits and risks of study participation. The patient will sign and receive a copy of an informed consent form (ICF) that was approved by the Institutional Review Board (IRB) before any study-specific procedure is performed.

An original signed ICF will be retained in the patient's source documentation at the site and a copy will be provided to the patient.

Written informed consent must be obtained from the patient before any study-related procedures are performed, and if there is a change in the study procedures during study participation.

7.4 Clinical Assessments

All clinical assessments will be collected as indicated in the Schedule of Events ([Appendix 1](#)).

7.4.1 Demographics

Demographic data including sex, age, race, and ethnicity will be collected.

7.4.2 Medical and Ophthalmic History

A complete medical history that includes all relevant medical and surgical history will be collected. A complete ophthalmic history will be collected.

7.4.3 Prior and Concomitant Medications

The name, dose, and frequency of all prescription and OTC medications that the subject is taking or has taken within 30 days prior to the Screening Visit must be recorded. All allowed and excluded medications should be recorded, including all prescription drugs, vitamins, supplements, and OTC medications. Generic drug names should be used preferentially.

7.4.4 Pregnancy Test

A urine pregnancy test will be performed at the Screening and Baseline Visits for WOCBP.

7.4.5 In-Office Investigational Product Administration

Refer to [Section 5.3.3](#) for a description of IP administration procedures.

IP administration must be performed at least 20 minutes after completion of CFS.

7.4.6 Investigational Product Tolerability Visual Analog Scale

Investigational product tolerability will be measured on a scale ranging from 0 (no discomfort) to 100 (severe discomfort; [Appendix 2](#)). Study staff will measure and record the VAS scores. Score cards will be retained for measurement confirmation.

7.4.7 Investigational Product Comfort Visual Analog Scale

Investigational product comfort will be measured using the American Society of Heating, Refrigerating and Air-conditioning Engineers (ASHRAE) 7-point VAS ([Beizaei 2012](#)) ranging from -3 to +3 ([Appendix 3](#)). The assessment will be conducted before IP administration (pre-dose) and 5, 15, 30, and 60 minutes post-IP administration, unless the score at 5 and 15 minutes is 0, in which case

the 30- and 60-minute assessments can be omitted. Study staff will measure and record the VAS scores. Score cards will be retained for measurement confirmation.

7.4.8 Eye Dryness Score Visual Analog Scale

Eye dryness will be measured using the EDS VAS ranging from 0 to 100 ([Appendix 4](#)). Study staff will measure and record the VAS scores. Score cards will be retained for measurement confirmation.

7.4.9 Ocular Discomfort Score Visual Analog Scale

Ocular discomfort will be measured using the ODS VAS ranging from 0 to 100 ([Appendix 5](#)). Study staff will measure and record the VAS scores. Score cards will be retained for measurement confirmation.

7.4.10 Symptom Assessment in Dry Eye Questionnaire

A modified SANDE instrument ([Schaumberg, 2007](#)) will be used to evaluate dry eye symptoms ([Appendix 6](#)). Subjects will respond to separate questions assessing frequency and severity of symptoms over the past week. Study staff will measure and record the SANDE. Score cards will be retained for measurement confirmation.

7.4.11 Unanesthetized Schirmer's Test

At all visits an unanesthetized Schirmer's test will be initiated in each eye at least 15 minutes after CFS. At Visits 1, 2 and 6 it will be repeated at least 20 ± 5 minutes after IP administration. ([Appendix 7](#))

Strips should be placed in each eye, right before left. After placement OU the 5-minute testing period will be initiated. Strips will be removed after 5 minutes, and the amount of wetting marked and the measurement recorded in mm by comparison to a ruler. Strips should be preserved to allow for measurement confirmation.

7.4.12 Best-Corrected Visual Acuity (and Refraction)

LogMAR VA must be assessed for each eye using a standard Early Treatment Diabetic Retinopathy Study (ETDRS) illuminated chart (on wall or stand) at 4 m. The procedure used will be consistent with the recommendations provided for using the ETDRS eye chart, which will be provided separately to the clinical site. Visual acuity should be evaluated at the beginning of each visit in the study (ie, prior to slit lamp examination). Visual acuity testing should be done with the most recent correction. Subjects will undergo manifest refraction at Screening according to the Investigator's standard of care. At any study visit if there is a 3-line or more reduction in VA since the prior BCVA was performed, a repeat refraction and BCVA should be performed.

7.4.13 Slit Lamp Biomicroscopy

The anterior-segment examination of each eye will be performed according to the Investigator's usual clinical technique. Magnification, lighting, and examiner should be consistent for each subject throughout the study. Biomicroscopy should be performed prior to pupil dilation. The examination should include an evaluation of the lids, conjunctiva, cornea, anterior chamber, iris/pupil (Screening

Visit only), and lens using a 4-point grading scale (0, none; 1, mild; 2, moderate; and 3, severe, as applicable).

7.4.14 Corneal Fluorescein Staining (CFS)

Sodium fluorescein will be delivered according to the instructions in into the conjunctival cul-de-sac of each eye followed by adequate blinking ([Appendix 8](#)). Staining will be measured 2 to 2½ minutes after instillation using the cobalt blue light of the slit lamp and a yellow Tiffen lens ([Appendix 9](#)). The modified NEI Grading Scale will be used to grade each of the 5 corneal zones using a 0 to 4 scale ([Lemp 1995](#)). The Investigator must review the grading scale at every examination when scoring the amount of staining.

7.4.15 Intraocular Pressure

All IOP assessments must be measured by Goldmann applanation tonometry. The tonometer calibration should be checked for accuracy within 1 month before screening the first subject for the study with measurements recorded and filed before the first subject is screened; calibration must be checked monthly thereafter throughout the study. Variation within ± 2 mmHg is acceptable. The fluorescein and anesthetic agents should remain consistent throughout the study. Intraocular pressure will be measured following biomicroscopy and always prior to dilation.

Two consecutive IOP measurements should be taken, with the right eye measured first. The applanation probe should be withdrawn between measurements. If the first 2 measurements differ by >2 mmHg, a third measurement will be taken. Repeat for the left eye.

At the Screening Visit, Goldmann applanation tonometry must be performed after the completion of the unanesthetized Schirmer's test and prior to randomization to run-in IP.

At the Baseline Visit, Goldmann applanation tonometry must be performed after the completion of the unanesthetized Schirmer's test and prior to randomization to IP assignment.

At Visit 6, Goldmann applanation tonometry must be performed after the completion of the unanesthetized Schirmer's test.

7.4.16 Anesthetized Schirmer's Test

Five minutes after the instillation of anesthetic drops strips should be placed in each eye, right before left. After placement OU the 5-minute testing period will be initiated. Strips will be removed after 5 minutes, and the amount of wetting marked and the measurement recorded in mm by comparison to a ruler. Strips should be preserved to allow for measurement confirmation.

7.4.17 Fundoscopy (Dilated Ophthalmoscopy)

Indirect dilated ophthalmoscopy will be performed on all subjects, UNLESS one of the below scenarios occur:

- Indirect dilated ophthalmoscopy was performed by a licensed eye professional within 6 months prior to Visit 1. In that case, it is not necessary to repeat ophthalmoscopy

- Indirect dilated ophthalmoscopy was performed by a licensed eye professional between 6 and 12 months prior to Visit 1. In that case, either direct undilated or indirect dilated ophthalmoscopy will be performed

Posterior segment examination of each eye will be performed according to the Investigator's preferred procedure. Magnification, lighting, and examiner should be consistent for each subject throughout the study. Ophthalmoscopy should be performed after pupil dilation. The examination should include evaluation and grading of the vitreous, macula, retinal vessels, peripheral retina, and optic disc using a normal/abnormal grading scale, as applicable.

7.4.18 Adverse Events

At each visit, the subject should be asked general questions such as, "How are you/your eyes feeling today? Have you had any changes since the last study visit?"

Any AE occurring after the first dose of IP will be recorded as an AE. Adverse events occurring during the Screening Visit prior to the first dose of IP will be noted in the medical history.

7.5 Study Activities

The Schedule of Events ([Appendix 1](#)) outlines the below events and procedures.

7.5.1 Screening Visit (Day -7 to 1 +2 days)

Procedures should be conducted in the following order:

- Informed consent
- Eligibility determination
- Demographics
- Medical/Ophthalmic history
- Concomitant medications
- Urine pregnancy test (WOCBP only)
- Eye Dryness Score VAS
- Ocular Discomfort Score VAS
- Investigational product ASHRAE 7-point comfort VAS (pre-dose)
- Best-corrected VA and refraction OU
- Slit lamp biomicroscopy OU
- Corneal fluorescein staining OU
- First unanesthetized Schirmer's test OU (≥ 15 minutes post-CFS)
- Intraocular pressure OU

- Assign run-in IP (vehicle)
- In-office IP (vehicle) administration OU (≥ 20 minutes post-CFS)
- Investigational product ASHRAE 7-point comfort VAS (5 ± 2 minutes post-dose)
- Symptom Assessment in Dry Eye questionnaire ($5 + 10$ minutes post-dose)
- Investigational product tolerability VAS ($5 + 10$ minutes post-dose)
- Investigational product ASHRAE 7-point comfort VAS (15 ± 2 minutes post-dose)
- Second unanesthetized Schirmer's test OU ($\geq 20 \pm 5$ minutes post-dose)
- Investigational product ASHRAE 7-point comfort VAS (30 ± 5 and 60 ± 5 minutes post-dose)
- Fundoscopy (indirect dilated ophthalmoscopy) OU
- Dispense run-in vehicle
- Adverse event assessment

7.5.2 Baseline/Randomization Visit (Day 1)

Procedures should be conducted in the following order:

- Eligibility determination
- Medical/Ophthalmic history
- Concomitant medications
- Collect run-in vehicle/compliance assessment
- Urine pregnancy test (WOCBP only)
- Eye Dryness Score VAS
- Ocular Discomfort Score VAS
- Investigational product ASHRAE 7-point comfort VAS (pre-dose)
- Best-corrected VA OU
- Slit lamp biomicroscopy OU
- Corneal fluorescein staining OU
- First unanesthetized Schirmer's test OU (≥ 15 minutes post-CFS)
- Anesthetized Schirmer's test OU
- Intraocular pressure OU

- Randomization
- In-office IP administration OU (≥ 20 minutes post-CFS)
- Investigational product ASHRAE 7-point comfort VAS (5 ± 2 minutes post-dose)
- Symptom Assessment in Dry Eye questionnaire ($5 + 10$ minutes post-dose)
- Investigational product tolerability VAS ($5 + 10$ minutes post-dose)
- Investigational product ASHRAE 7-point comfort VAS (15 ± 2 minutes post-dose)
- Second unanesthetized Schirmer's test OU ($\geq 20 \pm 5$ minutes post-dose)Investigational product ASHRAE 7-point comfort VAS (30 ± 5 and 60 ± 5 minutes post-dose)
- Anesthetized Schirmer's test OU (post final Investigational Product ASHRAE 7-point comfort VAS)
- Dispense IP
- Adverse event assessment

7.5.3 Visit 3 (Day 8 ± 1 day), Visit 4 (Day 15 ± 2 days), and Visit 5 (Day 22 ± 2 days)

Procedures should be conducted in the following order:

- Concomitant medications
- Collect IP/compliance assessment/dispense IP
- Eye Dryness Score VAS
- Ocular Discomfort Score VAS
- Investigational product ASHRAE 7-point comfort VAS (pre-dose)
- Best-corrected VA OU
- Slit lamp biomicroscopy OU
- Corneal fluorescein staining OU
- Unanesthetized Schirmer's test OU (≥ 15 minutes post-CFS)
- In-office IP administration OU (≥ 20 minutes post-CFS)
- Investigational product ASHRAE 7-point comfort VAS (5 ± 2 minutes post-dose)
- Symptom Assessment in Dry Eye questionnaire ($5 + 10$ minutes post-dose)
- Investigational product tolerability VAS ($5 + 10$ minutes post-dose)
- Investigational product ASHRAE 7-point comfort VAS (15 ± 2 minutes post-dose)

- Investigational product ASHRAE 7-point comfort VAS (30 ±5 and 60 ±5 minutes post-dose)
- Adverse event assessment

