4.4 Discontinuation of Treatment and Withdrawal of Subjects

The Investigator may withdraw a subject from the study for any of the following reasons:

- A serious or intolerable AE occurs
- A clinically significant change in systemic health
- The Sponsor or Investigator terminates the study
- The subject requests to be discontinued from the study

Withdrawal of subjects from the study will occur with completion of an Early Termination (ET) Visit to collect EOS data.

Subjects who use prohibited concomitant medications during the study will not be withdrawn from the trial. The data from subjects who use prohibited concomitant medications during the study will be included in the Modified Intention-to-Treat (mITT) analysis and excluded from the per-protocol analysis.

4.4.1 *Early Termination Visit*

Subjects who are withdrawn from the study should complete an ET Visit, with assessments completed in a comparable manner to an EOS Visit.

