4.5 Subject Replacement

Subjects who are withdrawn from the study will not be replaced.

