8.5 Recording of Adverse Events

All AEs should be reported starting after the first IP dose is administered (during the run-in period) and through 30 days after last dose of IP. The Sponsor may request follow-up on any unresolved AEs within 30 days after the final study visit.

All conditions present prior to receiving the IP should be documented as medical history. Information to be collected includes type of event, date of onset, date of resolution, and Investigator-specified assessment of severity and relationship to the IP.

While an AE is ongoing, changes in the severity (eg, worsening and improving) should be noted in the source documents but, when documenting the AE, only the total duration and greatest severity should be recorded in the electronic case report form (eCRF). Adverse events characterized as intermittent require documentation of onset and duration.

Pre-existing conditions (present before the start of the AE collection period) are considered concurrent medical conditions and should NOT be recorded as AEs. If the subject, however, experiences a worsening or complication of such a concurrent condition, the worsening or complication should be recorded as an AE. The Investigator should ensure that the AE term recorded captures the change in the condition (eg, ‘worsening of’).

Each AE should be recorded as a single diagnosis. Accompanying signs (including abnormal laboratory test values) or symptoms should NOT be recorded as additional AEs. Changes in laboratory test values are only considered to be AEs if they are judged to be clinically significant (ie, if some action or intervention is required or if the Investigator judges the change to be beyond the range of normal physiological fluctuation). If abnormal laboratory test values are the result of pathology for which there is an overall diagnosis (eg, increased creatinine in renal failure), only the diagnosis should be reported as an AE.

Pre-planned elective procedures (surgeries or therapies) known at the time of randomization that are performed to manage/treat conditions that existed prior to the subjects’ enrolling in the study (eg, elective periodontal surgery, elective hernia repair) should not be recorded as AEs but should be documented in the subject’s source documents. If a pre-planned procedure is performed early (eg, as an emergency) because the pre-existing condition worsens, the worsening condition should be captured as an AE.

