7.2.1.1. Adverse Events Occurring During the Run-In Period

Adverse events will be collected throughout the entirety of the study, including during the run-in period. If an AE begins during the run-in period and continues into the treatment period, then the AE will also be counted as a treatment-period event.

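### At Visits 2-6 the only listed adverse event enquiry comes after that visit's in-office dose, and events starting on Day 1 cannot be reliably placed before or after the first randomised dose from their onset date

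*Protocol*

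**What the plan says.** The list for each visit opens with the same instruction, "Procedures should be conducted in the following order", and at Visits 2-6 it ends with "Adverse event assessment". That item appears nowhere else in those lists. Appendix 1 marks an AE assessment at every visit, in its last row, with no footnote on timing relative to the dose.

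Protocol 7.4.18 describes the enquiry: "At each visit, the subject should be asked general questions such as" how the subject and the eyes are, and whether anything has changed since the previous visit. It does not say whether this comes before or after dosing.

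Protocol 8.5 starts AE recording at the first run-in dose and describes the record: "Information to be collected includes type of event, date of onset, date of resolution", plus severity and relationship. No clock time is named. SAP 2.3.1 computes study day from calendar dates. SAP 7.2.1 plans TEAE tables without defining TEAE. SAP 7.2.1.1 covers the carry-over case: "If an AE begins during the run-in period and continues into the treatment period", the event is also counted in the treatment period.

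**The concern.** A question about the time since the previous visit belongs before the next dose. Protocol 4.4 lets the investigator withdraw a subject when "A serious or intolerable AE occurs", but under the written order the information for that judgement is first sought after the subject has been dosed again. At Visit 2 it is sought after the subject has entered the randomised set, from which, under 4.5, "Subjects who are withdrawn from the study will not be replaced". Take-home product has also been handed over by then: dispensing is item 24 of 25 at Visit 2 and item 2 of 16 at Visits 3-5.

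Safety is the primary objective according to SAP 3.3 and 7.2, Protocol 1.4 reports no earlier human use in the US, and Protocol 1.5 names ocular discomfort as the main potential risk. Discomfort is a symptom that can come and go between visits, so an eye examination alone may not show it.

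Day 1 adds an attribution problem. Fluorescein, Schirmer's strips, anesthetic and tonometry all precede the first randomised dose on the same date, and each could plausibly cause a short-lived ocular event.

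**Working it through.** **Position of the steps.** Counting the items in 7.5.2 to 7.5.4, with the 30- and 60-minute comfort reading at Visit 2 taken as its own item (it is run together with the line before):

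| Visit | Randomisation | In-office dose | AE assessment | Items in list |
|---|---|---|---|---|
| 2 | 15 | 16 | 25 | 25 |
| 3-5 | none | 10 | 16 | 16 |
| 6 | none | 10 | 19 | 19 |

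**Delay from dose to AE enquiry, if the order is followed.**
- With the 60 ±5 minute comfort reading: at least 60 - 5 = 55 minutes.
- With the 30- and 60-minute readings omitted (allowed when the 5- and 15-minute scores are 0), Visits 3-5: at least 15 - 2 = 13 minutes.
- With them omitted, Visits 2 and 6: the second unanesthetized Schirmer's test starts no earlier than 20 - 5 = 15 minutes and takes 5. The anesthetized test then needs a 5-minute wait and 5 minutes of testing. 15 + 5 + 5 + 5 = 30 minutes at least.

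**Number of doses affected.** Visits 2-6 are 5 visits. With no dropout, 5 x 150 = 750 in-office doses. If the 150 - 138 = 12 subjects allowed for attrition all left straight after Visit 2 and received no further in-office dose, 150 + 4 x 138 = 702.

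**Do the earlier steps replace the enquiry?**
- EDS and ODS (every visit, before the dose) rate how the eyes feel now (Appendices 4 and 5). A resolved reaction does not show.
- SANDE covers the past week but is done after the dose.
- BCVA, slit lamp and staining (every visit) and IOP (before the dose at Visit 2) record vision, signs and pressure, not past symptoms.
- Eligibility and medical/ophthalmic history are repeated before the dose at Visit 2 only. Protocol 8.5 assigns history to conditions present before the IP, so a run-in reaction belongs in the AE record.
- Concomitant medications and the compliance check, with its query about missed doses (5.4), may bring an event to light but do not ask about one.

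**Which Day 1 events are ambiguous?**
1. Onset before Day 1: the onset date places the event in the run-in. No ambiguity.
2. Onset on Day 1 before the dose, still present after it: under SAP 7.2.1.1 it is counted in the treatment period even when classed as run-in. The period count is unaffected; the origin is lost.
3. Onset on Day 1 before the dose, resolved before it: by date alone this looks the same as a first-dose reaction that resolved that day. Here the count of first-dose events can be inflated.

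A case 3 event has three possible homes. Protocol 8.5 makes it an AE, since recording began in the run-in. The note in SAP 7.2.1 could send it to history, if study drug there means the randomised product. A date-based TEAE rule would count it against the randomised arm.

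**Home use on the morning of Visit 2.** Footnote [l] to Appendix 1, repeated under SAP Table 1, rules out a home dose on the mornings of Visits 2-6. Protocol 3.7 and 5.3.3 and SAP 2.2 name only Visits 3-6. These places do not match, so whether a run-in wipe could also precede the Day 1 dose depends on which is followed.

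**The case against.** The strongest reply is that nobody reaches dosing unexamined. Every visit has symptom scores and an eye examination first, and Visit 2 adds eligibility, history and IOP before randomisation. Nothing in 7.4.18 stops a site from asking on arrival, and an enquiry at the end is needed for post-dose events. This stands against any inference that subjects are dosed without a safety check. It does not answer the narrower point: none of these steps is an AE enquiry about the interval, and the written order does not require one before the dose.

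A reader might infer that Protocol 4.4 is contradicted. It is not. It says the investigator may withdraw a subject and does not tie that decision to the visit-end question. Subjects can ask to stop at any time, and serious events must be reported within 24 hours of site knowledge.

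A reader might also infer that events reported at the Day 1 visit cannot be divided between run-in and randomised product at all. Only onsets on the Day 1 date are ambiguous, and the cause is date-only recording and a missing TEAE rule as much as the order of the list. Protocol 8.5 gives its data items as inclusions, so a clock time is not ruled out, and the eCRF is not available to check.

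Finally, a reader might expect a loss of power or a bias between arms. The documents give no rate of run-in events that would lead to withdrawal, so no effect on attrition can be sized. The Day 1 pre-dose procedures precede randomisation and are the same for everyone, so their events should fall about equally on the three arms.

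**Conclusion.** The point holds within limits. At all five visits of the randomised period the only listed AE enquiry follows the in-office dose, by at least 55 minutes when the full comfort series is done and by at least 13 minutes otherwise. The enquiry follows randomisation at Visit 2 only. The figure of 750 doses is a no-dropout maximum and counts doses given before the question, not harm.

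The Day 1 problem is confined to events with onset on that date, and it affects the treatment-period count mainly for those that begin and resolve before the first randomised dose. The likely result is that absolute first-dose AE rates are blurred, with little effect on differences between arms. Both conclusions assume that sites follow the written order and that the eCRF records no onset time.

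This does not threaten the efficacy analysis. It is a weakness in how a study whose primary objective is safety collects its safety data, and it should be corrected because the correction is small.

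**What to change.** 1. In Protocol 7.5.2 to 7.5.4 and Appendix 1, list the AE enquiry twice: at the start of the visit with concomitant medications, before randomisation and the in-office dose, and again at the end for post-dose events.
2. On the AE form, for any onset on a visit day, record whether the event began before or after that visit's in-office dose.
3. In the SAP, define TEAE so that a Day 1 onset before the first randomised dose is classed as run-in, and state whether events carried over under 7.2.1.1 enter the TEAE tables.
4. Reconcile footnote [l] with Protocol 3.7 and 5.3.3 and with SAP 2.2 on home dosing before Visit 2.

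No change to any dose or withdrawal rule is proposed. The cost is a short repeated question, one eCRF field, and the amendment text, with no extra visit or test. If the visits have already taken place, item 3 can still be done before unmasking, using source notes for Day 1 onsets and showing separately those that cannot be classified.
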